  - Grade 3 tumor flare (defined as local pain, irritation or rash localized at sites of known or suspected tumor)
  - Grade 3 irAE that resolves to Grade 1 with corticosteroid therapy in  $\leq 3$  weeks (Part 1b ONLY)
  - A transient (resolves within 6 hr of onset) Grade 3 infusion-related AE (Part 1b ONLY)
- Any clinically meaningful Grade 3 non-hematologic laboratory value if:
  - Medical intervention (other than electrolyte repletion) is required to treat the patient, OR
  - The abnormality leads to hospitalization, OR
  - The abnormality persists for  $> 1$  week.

Hematologic DLTs:

- Grade  $\geq 3$  febrile neutropenia (ANC  $< 1.0 \times 10^9/L$  with either a single temperature  $\geq 38.3^\circ C$  or a sustained temperature of  $\geq 38^\circ C$  for more than 1 hr)
- Grade 4 neutropenia lasting  $> 7$  days
- Grade 4 anemia
- Grade 4 thrombocytopenia ( $< 25.0 \times 10^9/L$ )
- Grade 3 thrombocytopenia resulting in clinically significant bleeding or requiring platelet transfusion
- Any other  $\geq$  Grade 3 hematologic toxicity

In addition to the DLTs defined above, clear evidence of urea cycle inhibition (e.g., an increase in fasting urinary orotic acid (OA) to  $\geq 10X$  the ULN, any OA value of  $> 40X$  ULN (fasting or non-fasting) or symptomatic hyperammonemia) would also be considered a dose-limiting event and will be monitored closely (see below for urinary OA rationale). Finally, achieving a maximum exposure threshold of an  $AUC_{0-12hr}$  that exceeds  $100 \mu g \cdot hr/mL$  in one patient will limit dose escalation. This exposure is approaching the top of the exposures that were well tolerated in preclinical GLP toxicology studies. Exposure in excess of this threshold will be treated the same as a DLT with regard to the dose escalation rules and definition of the MTD described in Section 5.1.1.

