Since this protocol was first written, additional literature sources have been identified in which elevation of urinary OA have been studied in healthy people who are carriers of a single urea cycle gene defect (UCD). In one study, 24 individuals that were carriers of a single defective gene for ornithine transcarbamylase (OTC) were studied (Nagasaka 2013). These individuals were considered healthy without clinical evidence of urea cycle dysfunction. Fasting urinary OA was elevated in all of these individuals, with a mean level of 11  $\mu\text{mol}/\text{mmol}$  creatinine that ranged from 5 to 23  $\mu\text{mol}/\text{mmol}$  creatinine. In addition, other studies in similar populations of healthy individuals with a known or presumed single defective urea cycle gene have demonstrated that urinary OA elevates significantly following a meal (due to the increased processing of ammonia by the liver following a protein meal), as compared to normal individuals with a fully intact urea cycle in whom there is a minimal change in urinary OA following a meal. Following a meal, the urinary OA in these healthy UCD carriers rose as high as 62  $\mu\text{mol}/\text{mmol}$  creatinine (Goldstein 1974).

Based on the clinical experience to date with INCB001158 and the more extensive literature evidence of elevations in urinary OA in healthy UCD, the management of elevated urinary OA

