has been updated in the protocol. Given the variability of urinary OA following a meal in healthy UCD carriers, separate thresholds have been defined for fasting patients (i.e., patients tested predose) versus those that have eaten (i.e., patients tested 6 hr postdose). In addition, since urinary OA elevations may be variable and have not been associated with evidence of clinically significant urea cycle inhibition, re-testing of urinary OA while the patient continues to receive INCB001158 is recommended in patients that have no evidence of clinically significant urea cycle inhibition (i.e., asymptomatic, plasma ammonia/BUN without significant change from baseline) in order to confirm that the elevation was not spurious. For elevations of urinary OA of  $> 15 \mu\text{mol}/\text{mmol}$  creatinine ( $>10\text{X}$  ULN) in fasting patients, dose reduction is recommended. This value is within the range of urinary OA elevations that were seen in the cohort of 24 healthy UCD carriers tested while fasting in Nagasaka *et al* (2013). For patients that are not fasting, higher elevations can be expected, based on the elevations in UCD carriers following a meal. Therefore, for elevations of urinary OA of  $> 60 \mu\text{mol}/\text{mmol}$  creatinine ( $40\text{X}$  ULN) at any time, dose reduction is recommended.

In summary, there has been no evidence of clinically significant inhibition of the urea cycle to date. Two patients have had asymptomatic transient elevations in urinary OA, a sensitive biomarker of hepatic urea cycle inhibition, that were not associated with changes in plasma ammonia or BUN, but were dose reduced based on the original protocol defined urinary OA threshold of  $5\text{X}$  ULN. Based on this clinical experience and a more extensive evaluation of the published data in healthy carriers of UCD genes, the approach to managing INCB001158 study drug in response to elevations in urinary OA has been changed in the current amendment. All of these data and the current management approach have been reviewed by an external clinical expert in the management of patients with UCD [REDACTED].

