*These parameters are only guidelines and are not intended to supersede the clinical judgment of the treating physician.* Investigators should err on the side of caution in the setting of potential ir-AEs. Investigators should contact the Medical Monitor if 1) a dose modification is planned, 2) systemic immunosuppression is required (NB: if immediate systemic immunosuppression is required, please DO NOT delay the start of immunosuppressive therapy in order to speak with the Medical Monitor), or 3) there is a preference to deviate from the guidelines for the management of AEs or dose modifications. Holding of the study treatment and study discontinuation for both non-hematological and hematological toxicities will be based on the Principal Investigator's judgment following discussion with the Medical Monitor.

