**Table 12.1-1: INCB001158 Dose Modification Guidelines for Adverse Events in Patients Receiving INCB001158 (All Parts)**

Adverse Reaction	Severity	Management	Study Drug Dose Modification
Evidence of urea cycle inhibition	
 
Fasting urinary orotic acid > 2 X and <math>\leq</math> 10 X ULN
 
Any urinary orotic acid > 2 X and <math>\leq</math> 40 X ULN
 
	
 
Re-test fasting urinary orotic acid 1 week later.
 
	
 
None.
 

	
 
Ammonia 2 X ULN and 2 X baseline (repeated measurements or with symptoms)
 
Fasting urinary orotic acid > 10 X ULN
 
Any urinary orotic acid > 40 X ULN
 
BUN < 50% LLN
 
	
 
See Section 12.1.3.3 for management of hyperammonemia.
 
	
 
Interrupt study drug.
 
Consider restarting (at a lower dose) in consultation with Medical Monitor.
 

Study drug-related creatinine increase  (patients with CrCl 30-49 mL/min at baseline)	Grade 2 (> 1.5-3.0 X baseline)	Weekly testing of serum creatinine during interruption of study drug.	
 
Interrupt study drug.
 
1st event: Restart at same dose upon resolution to <math>\leq</math> Grade 1.
 
2nd event: Restart at 25 mg BID upon resolution to <math>\leq</math> Grade 1.
 

	Grade 3 (> 3.0 baseline) or 4 (dialysis indicated)	Weekly testing of serum creatinine during interruption of study drug.	
 
Interrupt study drug and do weekly serum creatinine testing and urinalysis until serum creatinine returns to <math>\leq</math> Grade 1. Restart study drug at 25 mg BID.
 
If after 4 weeks the serum creatinine has not recovered to <math>\leq</math> Grade 1, permanently discontinue study drug.
 
If after restarting study drug the toxicity reoccurs, permanently discontinue study drug.
 

**Table 12.1-1: INCB001158 Dose Modification Guidelines for Adverse Events in Patients Receiving INCB001158 (All Parts) (Continued)**

Adverse Reaction	Severity	Management	Study Drug Dose Modification

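### Table 12.1-1 places a fasting orotic acid above 10X and up to 40X ULN in both the no-change row and the interrupt row

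*Protocol*

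**What the plan says.** The evidence-of-urea-cycle-inhibition entry in Protocol Table 12.1-1 applies to all Parts and has two rows.

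- **Row 1** lists fasting orotic acid above 2X and up to 10X ULN, and *any* orotic acid above 2X and up to 40X ULN. The management is "Re-test fasting urinary orotic acid 1 week later" and the dose modification is none.
- **Row 2** lists fasting orotic acid above 10X ULN and any orotic acid above 40X ULN, alongside ammonia and BUN criteria. The drug is interrupted, and the site is told to "Consider restarting (at a lower dose) in consultation with Medical Monitor".

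The orotic acid rationale in Section 5.1.2 says that "separate thresholds have been defined for fasting patients (i.e., patients tested predose) versus those that have eaten". For a value above 15 µmol/mmol creatinine (10X ULN) it says that "in fasting patients, dose reduction is recommended", and it gives the same advice above 60 µmol/mmol (40X ULN) at any time. It also says that "re-testing of urinary OA while the patient continues to receive INCB001158 is recommended" when there is no clinically significant urea cycle inhibition, to rule out a spurious value.

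Section 12.1.3.1 limits the force of the table: "These parameters are only guidelines and are not intended to supersede the clinical judgment of the treating physician".

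**The concern.** The *any* bullet in row 1 is not confined to samples taken after food. Read as printed, it takes in fasting samples up to 40X ULN, while row 2 claims fasting samples from just above 10X. A site with a fasting result of 15X ULN can point to a row that changes nothing and to a row that stops the drug.

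Orotic acid is the protocol's early marker of the drug's on-target toxicity; Section 12.1.1 reports that in rats it rose more than 1,000-fold before any sign of toxicity. The threshold at which treatment is held should have one reading.

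There may also be a small effect on the safety tables. Under Section 16.1.1 a laboratory abnormality counts as an adverse event if, among other things, it requires a change in study treatment, and SAP Section 8.2.3 counts events leading to interruption. The same asymptomatic value could be recorded differently at two sites. This is inferred from the rules and no case is documented. The values themselves are listed in either case (SAP Appendix A, Listing 2.85).

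**Working it through.** **Units.** Section 5.1.2 equates 15 µmol/mmol creatinine with 10X ULN and 60 with 40X ULN. 15/10 = 1.5 and 60/40 = 1.5, so the two thresholds agree on a ULN of 1.5 µmol/mmol.

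**Row membership as printed.** Let x be orotic acid divided by ULN, using the orotic acid bullets only.

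- Row 1 is met if (fasting and 2 < x ≤ 10) or (2 < x ≤ 40).
- Row 2 is met if (fasting and x > 10) or (x > 40).

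For a fasting sample both hold when 2 < x ≤ 40 and x > 10, that is 10 < x ≤ 40. Multiplying by 1.5 gives above 15 and up to 60 µmol/mmol. For a non-fasting sample both would need x ≤ 40 and x > 40, which is impossible.

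| x (multiple of ULN) | µmol/mmol (x × 1.5) | Fasting: row 1 | Fasting: row 2 | Non-fasting: row 1 | Non-fasting: row 2 |
|---|---|---|---|---|---|
| 5 | 7.5 | yes | no | yes | no |
| 10 | 15 | yes | no | yes | no |
| 10.1 | 15.15 | **yes** | **yes** | yes | no |
| 15 | 22.5 | **yes** | **yes** | yes | no |
| 40 | 60 | **yes** | **yes** | yes | no |
| 40.1 | 60.15 | no | yes | no | yes |

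**Which row was meant.** Three pieces of text point to row 2.

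1. If *any* in row 1 included fasting samples, the row 1 fasting bullet (up to 10X) would be redundant.
2. Section 5.1.2 sets separate fasting and fed thresholds and recommends a dose reduction above the fasting one.
3. Row 1 asks for a fasting re-test, which suits follow-up of a sample taken after food.

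**Row membership after the change.** With the second row 1 bullet limited to non-fasting or unknown status:

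- fasting, 2 < x ≤ 10: row 1 only;
- fasting, x > 10: row 2 only;
- non-fasting or unknown, 2 < x ≤ 40: row 1 only;
- any sample, x > 40: row 2 only.

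On orotic acid alone there is then no overlap and no gap above 2X. The unknown category is needed because the footnotes to Attachments 2A to 2C let the predose sample be collected at any time before dosing, so fasting status may be uncertain.

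**Secondary comparison.** The re-testing advice in Section 5.1.2 depends on the absence of symptoms and of significant ammonia or BUN change, and states no orotic acid range. In row 2 the ammonia criterion asks for repeated measurements or symptoms, but the orotic acid bullets have no confirmation step. One text allows a repeat on drug; the other interrupts on the first value.

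**The case against.** The strongest reply is that the overlap has only one sensible reading. That is right about intent, for the reasons above. It is also true that the gloss of *any* as covering both sample types ("ULN (fasting or non-fasting) or symptomatic hyperammonemia) would also be considered a dose-limiting event") belongs to the 40X dose-limiting event and cannot simply be carried into row 1. The point therefore rests on the unrestricted word in row 1 itself.

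A second reply is that the table is guidance and that Section 12.1.3.1 calls for Medical Monitor contact. The guidance status stands and limits the effect. The contact is a weaker safeguard: it is triggered by a planned dose modification, a need for systemic immunosuppression, or a wish to deviate. A site that applies row 1 plans no modification and does not think it is deviating, so the call need not happen.

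A reader might infer more than the documents support:

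- **Three competing actions (interrupt, reduce, re-test).** Interrupting and then considering a lower dose is one way to carry out a reduction. Footnotes to Tables 10.1-3 and 10.1-4 describe a patient reduced from 150 to 100 mg BID after a 4-day interruption. Only the question of confirming first remains.
- **A threshold set wrongly because healthy carriers exceed it.** Section 5.1.2 reports fasting carrier values (µmol/mmol "creatinine that ranged from 5 to 23"), notes that the 15 µmol/mmol threshold lies in that range, and still recommends a reduction. That is a deliberate choice.
- **A material mismatch between at-least-10X for the dose-limiting event and above-10X in the table.** It matters only at exactly 10X and only for escalation decisions. Section 10.2.2.1 describes the escalation parts as completed.

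**Conclusion.** The point holds as a minor error of wording. As printed, fasting orotic acid above 10X and up to 40X ULN (above 15 and up to 60 µmol/mmol creatinine) meets both rows of Table 12.1-1, although the interrupt row was clearly intended. The tension between the re-test advice in Section 5.1.2 and row 2 is secondary.

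The practical effect is probably small. Section 10.1.12 reports no significant change at 50 or 100 mg BID, and 100 mg BID is the RP2D; elevations occurred in 2 of 3 patients at 150 mg BID. How many fasting values fell in the overlap cannot be stated, because Table 10.1-5 was not in the text available for this review. Part of the Section 5.1.2 rationale was also unavailable, so the verdict assumes that no precedence rule stands there. Nothing here shows that any patient was mishandled, and no sample size or error rate is affected.

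**What to change.** 1. In row 1 of Table 12.1-1, replace the second bullet with: *Urinary orotic acid > 2 X and ≤ 40 X ULN in a sample that is non-fasting or of unknown fasting status*. Row 1's fasting re-test then settles the status of an uncertain sample within a week.
2. Align Section 5.1.2 with row 2 on whether a first fasting value above 10X, without symptoms and with stable ammonia and BUN, is confirmed on drug or leads directly to interruption. The same sentence should cover values above 40X. Which policy to adopt is for the sponsor's clinical team; the two texts should simply agree.

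The cost is one bullet in the table and a sentence or two in Section 5.1.2. No scheduled visit, sample size or planned analysis changes. If confirmation on drug is chosen, it adds a repeat urine sample per event, as row 1 already does.

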### 12.1.2 Pembrolizumab (Patients Enrolled in Parts 1b, 1c, and 3)

Pembrolizumab is a potent humanized immunoglobulin G4 (IgG4) monoclonal antibody (mAb) with high specificity of binding to the programmed cell death 1 (PD-1) receptor, thus inhibiting its interaction with programmed cell death ligand 1 (PD-L1) and programmed cell death ligand 2 (PD-L2). Based on preclinical in vitro data, pembrolizumab has high affinity and potent receptor blocking activity for PD-1. Pembrolizumab has an acceptable preclinical safety profile and is in clinical development as an intravenous (IV) immunotherapy for advanced malignancies.

Keytruda™ (pembrolizumab) is indicated for the treatment of patients across a number of indications. For more details on specific indications refer to the Investigator brochure.

The safety profile of pembrolizumab is fully described in the pembrolizumab Label/Investigator's Brochure and primarily consists of immune-related adverse events (ir-AEs) due to activation and proliferation of T-cells. Ir-AEs can affect any organ or tissue, but most frequently occur in the skin (rash), gastrointestinal system (diarrhea/colitis), liver (hepatitis), lungs (pneumonitis), endocrine system (endocrinopathies due to inflammation of the pituitary, thyroid and adrenals), and kidneys (nephritis). The management of these toxicities is described in the pembrolizumab Label/Investigator's Brochure but generally includes holding drug for moderate (Grade 2) toxicities and using systemic immunosuppression for severe (Grade 3/4) or prolonged moderate (> 1 week) toxicities. Additional immunosuppression (e.g., anti-TNF $\alpha$  therapy, infliximab) may be used if IV steroids are ineffective.

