Study drug-related creatinine increase  (patients with CrCl > 50 mL/min at baseline)	Grade 2 (> 1.5-3.0 X baseline OR > 1.5-3.0 X ULN)	Weekly testing of serum creatinine during interruption of study drug.	
 
Interrupt study drug.
 
1st event: Restart at same dose upon resolution to ≤ Grade 1.
 
2nd event: Restart at 25 mg BID upon resolution to ≤ Grade 1.
 

	Grade 3 (> 3.0 baseline; > 3.0-6.0 X ULN) or 4 (> 6.0 X ULN)	Weekly testing of serum creatinine during interruption of study drug.	
 
Interrupt study drug and do weekly serum creatinine testing and urinalysis until serum creatinine returns to ≤ Grade 1. Restart study drug at 25 mg BID.
 
If after 4 weeks the serum creatinine has not recovered to ≤ Grade 1, permanently discontinue study drug.
 
If after restarting study drug the toxicity reoccurs, permanently discontinue study drug.
 

Suspected immune-related adverse event (irAE) including: 
 
Colitis
 
Pneumonitis
 
Dermatitis
 
Hepatitis
 
Hypophysitis
 
Adrenal insufficiency
 
Type I diabetes mellitus
 
Nephritis
 
	Grade 1	
 
Symptomatic therapy, as appropriate
 
	No change
	Grade 2	
 
If > 5 days, 0.5 to 1 mg/kg/day prednisone. If worsening or no improvement, increase to 1 to 2 mg/kg/day prednisone equiv. and consider IV.
 
	
 
Interrupt study drug.
 
1st event: Restart at same dose upon resolution to ≤ Grade 1.
 
2nd event: Restart one dose level lower for second event of the same AE.
 

	Grade 3	
 
1 to 2 mg/kg/day prednisone equiv. Consider IV.
 
	
 
Interrupt study drug.
 
1st event: Consider restarting at next lower dose level upon resolution to ≤ Grade 1.
 
2nd event: Permanently discontinue.
 

	Grade 4	
 
1 to 2 mg/kg/day prednisone equiv. Consider IV.
 
	
 
Permanently discontinue.
 

**Table 12.1-1: INCB001158 Dose Modification Guidelines for Adverse Events in Patients Receiving INCB001158 (All Parts) (Continued)**

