Adverse Reaction	Severity	Management	Study Drug Dose Modification
All others	Grade 1	Symptomatic therapy, as appropriate.	No change.
	Grade 2	Symptomatic therapy, as appropriate.	
 
Interrupt study drug.
 
1st event: Restart at same dose upon resolution to <math>\leq</math> Grade 1.
 
2nd event: Restart one dose level lower for second event of the same AE.
 

	Grade 3	Symptomatic therapy, as appropriate.	
 
Interrupt study drug.
 
1st event: Consider restarting at next lower dose level upon resolution to <math>\leq</math> Grade 1.
 
2nd event: Permanently discontinue.
 

	Grade 4	Symptomatic therapy, as appropriate.	
 
Permanently discontinue.
 

 For creatinine increases that are unrelated to study drug (e.g. obstructive uropathy) INCB001158 may be continued at a dose appropriate for the new CrCl (as calculated by the Cockcroft-Gault formula) as follows:

- CrCl > 50 mL/min: Continue INCB001158 at 100 mg BID.
- CrCl 30-49 mL/min: Reduce INCB001158 to 50 mg BID.
- CrCl < 30 mL/min: Hold INCB001158 and restart once CrCl > 30 mL/min as specified above.

**Table 12.1-2: Dose Modification and Toxicity Management Guidelines for Immune-Related Adverse Events Associated With Pembrolizumab (Parts 1b, 1c, and 3)**

General instructions				
1. Severe and life-threatening irAEs should be treated with IV corticosteroids followed by oral steroids. Other immunosuppressive treatment should begin if the irAEs are not controlled by corticosteroids. 2. Pembrolizumab must be permanently discontinued if the irAE does not resolve or the corticosteroid dose is not $\leq 10$ mg/day within 12 weeks of the last pembrolizumab treatment. 3. The corticosteroid taper should begin when the irAE is $\leq$ Grade 1 and continue at least 4 weeks. 4. If pembrolizumab has been withheld, pembrolizumab may resume after the irAE decreased to $\leq$ Grade 1 after corticosteroid taper.				
irAEs	Toxicity Grade (CTCAE V4.0)	Action With Pembrolizumab	Corticosteroid and/or Other Therapies	Monitoring and Follow-up

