Pneumonitis	Grade 2	Withhold	
 
Administer corticosteroids (initial dose of 1 - 2 mg/kg prednisone or equivalent) followed by taper
 
Add prophylactic antibiotics for opportunistic infections
 
	
 
Monitor participants for signs and symptoms of pneumonitis
 
Evaluate participants with suspected pneumonitis with radiographic imaging and initiate corticosteroid treatment
 

	Recurrent Grade 2, Grade 3 or 4	Permanently discontinue		
Diarrhea / Colitis	Grade 2 or 3	Withhold	
 
Administer corticosteroids (initial dose of 1 - 2 mg/kg prednisone or equivalent) followed by taper
 
	
 
Monitor participants for signs and symptoms of enterocolitis (ie, diarrhea, abdominal pain, blood or mucus in stool with or without fever) and of bowel perforation (ie, peritoneal signs and ileus)
 
Participants with <math>\geq</math>Grade 2 diarrhea suspecting colitis should consider GI consultation and performing endoscopy to rule out colitis
 
Participants with diarrhea/colitis should be advised to drink liberal quantities of clear fluids. If sufficient oral fluid intake is not feasible, fluid and electrolytes should be substituted via IV infusion
 

	Recurrent Grade 3 or Grade 4	Permanently discontinue		

**Table 12.1-2: Dose Modification and Toxicity Management Guidelines for Immune-Related Adverse Events Associated With Pembrolizumab (Parts 1b, 1c, and 3) (Continued)**

irAEs	Toxicity Grade (CTCAE V4.0)	Action With Pembrolizumab	Corticosteroid and/or Other Therapies	Monitoring and Follow-up
AST or ALT elevation or Increased Bilirubin	Grade 2 a	Withhold	
 
Administer corticosteroids (initial dose of 0.5 - 1 mg/kg prednisone or equivalent) followed by taper
 
	
 
Monitor with liver function tests (consider weekly or more frequently until liver enzyme value returned to baseline or is stable)
 

	Grade 3 b or 4 c	Permanently discontinue	
 
Administer corticosteroids (initial dose of 1 - 2 mg/kg prednisone or equivalent) followed by taper
 
	

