In addition, patients with severe enterocolitis that are receiving INCB001158 monotherapy will have INCB001158 permanently discontinued, whereas, for patients receiving INCB001158/pembrolizumab combination, pembrolizumab will be permanently discontinued and INCB001158 will be withheld. Restarting INCB001158 may be considered in INCB001158/pembrolizumab combination patients if enterocolitis is not a toxicity associated with monotherapy INCB001158.

In patients with moderate enterocolitis, pembrolizumab should be withheld and antidiarrheal treatment should be started. If symptoms are persistent for more than one week, systemic corticosteroids should be initiated (e.g., 0.5 mg/kg/day of prednisone or equivalent). When symptoms improve to Grade 1 or less, corticosteroid taper should be started and continued over at least 1 month. Regarding guidelines for continuing treatment with INCB001158 and pembrolizumab, see [Table 12.1-2](#).

All patients who experience diarrhea should be advised to drink liberal quantities of clear fluids. If sufficient oral fluid intake is not feasible, fluid and electrolytes should be substituted via IV infusion.

**Nausea/vomiting:** Nausea and vomiting should be treated aggressively, and consideration should be given in subsequent cycles to the administration of prophylactic antiemetic therapy according to standard institutional practice. Patients should be strongly encouraged to maintain liberal oral fluid intake. Since nausea/vomiting can be a symptom of hyperammonemia, there should be a low threshold to test plasma ammonia levels for patients with nausea, vomiting, or new onset anorexia.

**Anemia:** Transfusions and/or erythropoietin may be utilized as clinically indicated for the treatment of anemia, but should be clearly noted as concurrent medications.

**Neutropenia:** Prophylactic use of colony-stimulating factors including Granulocyte Colony-Stimulating Factor (G-CSF), pegylated G-CSF or Granulocyte Macrophage Colony-Stimulating Factor (GM-CSF) is not allowed in this study. Therapeutic use of G-CSF is allowed in patients with Grade 3-4 febrile neutropenia.

**Thrombocytopenia:** Transfusion of platelets may be used if clinically indicated. Idiopathic thrombocytopenic purpura (ITP) should be ruled out before initiation of platelet transfusion.

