#### 16.1.2 Reporting

Adverse events that begin or worsen after informed consent should be recorded on the Adverse Events form of the eCRF. Conditions that were already present at the time of informed consent should be recorded on the Medical History form in the eCRF. Monitoring for the occurrence of new AEs should be continued for up to 30 days after the last dose of study treatment or until the start of new anticancer therapy, whichever occurs first. Adverse events (including laboratory abnormalities that constitute AEs) should be described using a diagnosis whenever possible rather than by individual underlying signs and symptoms. When a clear diagnosis cannot be identified, each sign or symptom should be reported as a separate AE.

The term "disease progression" should be recorded as an AE/SAE only if there are no other identifiable AEs/SAEs associated with the disease progression at the time of reporting. For events associated with disease progression, the relevant signs and symptoms should be reported using a diagnosis whenever possible rather than individual underlying signs and symptoms. When a clear diagnosis cannot be identified, each sign or symptom should be reported as a separate AE. If the events resulting from disease progression meet the criteria for an SAE (eg, resulted in hospitalization, a life-threatening event, or death), the specific event(s) should be reported as an SAE(s) as described in Section 16.3.2. In both cases (ie, AEs or SAEs related to disease progression), it should be indicated that each event (reported as a diagnosis or as signs and symptoms) is related to disease progression on the Adverse Events form of the eCRF.

The severity of AEs will be assessed using CTCAE v4.03 Grades 1 through 5. If an event is not classified by CTCAE, the severity of the AE will be graded according to the scale below to estimate the grade of severity:

Grade 1	Mild; asymptomatic or mild symptoms; clinical or diagnostic observations only; intervention not indicated.
Grade 2	Moderate; minimal, local, or noninvasive intervention indicated; limiting age-appropriate activities of daily living.
Grade 3	Severe or medically significant but not immediately life-threatening; hospitalization or prolongation of hospitalization indicated; disabling; limiting self-care activities of daily living.
Grade 4	Life-threatening consequences; urgent intervention indicated.
Grade 5	Fatal

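### For a first Grade 3 enterocolitis, Section 12.1.3.3 and the dose-modification tables give opposite restart instructions for monotherapy INCB001158 and for combination pembrolizumab

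*Protocol*

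**What the plan says.** Three places in the protocol cover the same event.

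- **Section 12.1.3.3, diarrhea paragraphs.** On monotherapy, "patients with severe enterocolitis that are receiving INCB001158 monotherapy will have INCB001158 permanently discontinued". On combination, "pembrolizumab will be permanently discontinued and INCB001158 will be withheld". INCB001158 may then be restarted on combination "if enterocolitis is not a toxicity associated with monotherapy INCB001158"; no restart dose is given.
- **Table 12.1-1, suspected immune-related events.** The table applies to all Parts and the row names colitis. At Grade 3, first event: interrupt, then "Consider restarting at next lower dose level upon resolution to ≤ Grade 1". A permanent stop is reserved for a second Grade 3 event or for Grade 4.
- **Table 12.1-2, diarrhea/colitis row and general instructions.** Pembrolizumab is withheld at Grade 2 or 3 and permanently stopped only for "Recurrent Grade 3 or Grade 4". General instruction 4 begins "If pembrolizumab has been withheld, pembrolizumab may resume after the irAE decreased to" and goes on to require Grade 1 or less after the corticosteroid taper.

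On severity, Section 12.1.2 refers to "systemic immunosuppression for severe (Grade 3/4" toxicities and equates moderate with Grade 2. On routing, Section 12.1.3.1 says that immune-related events on combination therapy should be handled by the INCB001158 and pembrolizumab guidelines in Tables 12.1-1 and 12.1-2 respectively. For INCB001158 generally, it says only that dose-modification guidelines are found in Table 12.1-1.

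**The concern.** The rule decides whether a patient may be rechallenged after a severe bowel toxicity. An investigator who opens the table finds that a restart is permitted. One who opens the supportive-care text finds a permanent stop. Both texts are current and written for the same patients. A restart allowed by the table would therefore be at odds with the text, and sites could reasonably act differently after identical events. What is at stake is patient safety and consistent conduct across sites. Sample size, error rates and planned estimates do not depend on it.

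**Working it through.** No arithmetic applies, so the check compares the texts.

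**Step 1: is a first Grade 3 event severe?** Section 12.1.2 treats Grade 3/4 as severe and Grade 2 as moderate, and Section 12.1.3.3 handles moderate enterocolitis in a separate paragraph. A first Grade 3 enterocolitis therefore falls under the severe text.

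**Step 2: compare the instructions for a first Grade 3 event.**

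| Drug and regimen | Section 12.1.3.3 | Table | Relation |
|---|---|---|---|
| INCB001158, monotherapy | Permanent stop | 12.1-1: interrupt, may restart one level lower | Contradiction |
| Pembrolizumab, combination | Permanent stop | 12.1-2: withhold, may resume after recovery and taper | Contradiction |
| INCB001158, combination | Withhold; restart may be considered only if enterocolitis is not a monotherapy toxicity | 12.1-1: may restart one level lower | Condition missing from the table |

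**Step 3: what this means in dose.** For a monotherapy patient at the recommended dose of 100 mg BID, the next lower level in Table 5.1-1 is 75 mg BID. The choice is between no further INCB001158 and up to 75 mg BID. For pembrolizumab it is between no further infusion and a return to 200 mg every 3 weeks.

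**Step 4: does any sentence decide between them?**

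- *Combination:* Section 12.1.3.1 directs management to the two tables, which points to the table side of both combination cases. Section 12.1.3.3, a later passage specific to enterocolitis, still states a different rule and does not mention that direction.
- *Monotherapy:* Section 12.1.3.1 only gives Table 12.1-1 as the place where the guidelines are found. No sentence ranks that table against Section 12.1.3.3.
- *Internal cross-reference:* Section 12.1.3.3 refers to Table 12.1-2 for continuing both drugs, but does so in the moderate-enterocolitis paragraph, and that table has no INCB001158 action column.

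**Step 5: is the Section 12.1.3.3 text simply obsolete?** Attachment 12 records that Table 12.1-2 was updated in the current amendment and lists no matching edit to Section 12.1.3.3. That is consistent with a paragraph left unaligned, but it is an inference. Against it, Section 12.1.3.2 still provides for restarting INCB001158 after pembrolizumab has been permanently stopped, which is the sequence Section 12.1.3.3 describes. The text cannot safely be treated as superseded.

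**The case against.** The best defence is that these are guidelines with safeguards around them. Section 12.1.3.1 says that they do not override the treating physician's judgment, urges caution with possible immune-related events, and asks for Medical Monitor contact when a dose modification or a deviation is planned. Section 12.1.3.3 asks for immediate discussion of any immune-related event of Grade 2 or higher. Section 12.1.3.2 requires consultation before restart after an interruption of more than 4 weeks. Pembrolizumab would usually meet that condition, because the Table 12.1-2 taper starts only at Grade 1 or less and lasts at least 4 weeks. A permanent stop also satisfies both texts in every case. All of this stands and lowers the risk. It does not tell the Medical Monitor which instruction is the protocol's.

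Some stronger readings are tempting but not supported:

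- *That nothing says which source governs.* For combination patients Section 12.1.3.1 does point to the tables. The unranked case is monotherapy.
- *That all three cases contradict.* For INCB001158 on combination, both sources are permissive and can be applied together. The table only lacks the condition.
- *That the severity scale in Section 16.1.2 settles what severe means, including at Grade 4.* Its Grade 3 entry reads "Severe or medically significant but not immediately life-threatening", but the scale is a fallback for events that CTCAE does not classify, and Table 12.1-2 grades by CTCAE. The reading here rests on Section 12.1.2.
- *That the preliminary safety table shows how often this will arise.* Table 10.1-2 covers 23 patients, and Section 10.1.12 presents it as single-agent data. It says nothing about combination, where two of the three cases lie.
- *That a restart allowed by a table would breach a binding rule.* Both sources are described as guidelines.

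**Conclusion.** The point holds in a limited form. For a first Grade 3 enterocolitis, Section 12.1.3.3 contradicts Table 12.1-1 for monotherapy INCB001158 and Table 12.1-2 for combination pembrolizumab. For combination INCB001158 the table omits one restart condition. The protocol routes combination patients to the tables while leaving an unaligned paragraph in place; for monotherapy it settles nothing.

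This rests on reading severe as including Grade 3, as Section 12.1.2 does, and on the documents alone. Section 12.1.3.3 is to be used together with the pembrolizumab label, which was not available. The number of patients affected cannot be estimated from the documents, and no statistical figure changes. The weight is minor to should-fix: opposite instructions on rechallenge after severe colitis are worth correcting, but Medical Monitor involvement already reduces the practical risk.

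**What to change.** State one rule per drug and regimen, in both places.

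1. **Monotherapy INCB001158.** Add an enterocolitis exception to the immune-related row of Table 12.1-1: Grade 3 or 4 on monotherapy, permanently discontinue. This keeps the stricter rule of Section 12.1.3.3.
2. **Combination INCB001158.** In the same row: first Grade 3, withhold, and restart one dose level lower after recovery to Grade 1 or less only if enterocolitis is not a toxicity of INCB001158 monotherapy; second Grade 3 or any Grade 4, permanently discontinue. This carries the condition into the table and supplies the restart dose missing from the text.
3. **Pembrolizumab.** Replace the severe-enterocolitis dosing sentences in Section 12.1.3.3 with a reference to the exception above for INCB001158 and to the diarrhea/colitis row of Table 12.1-2 for pembrolizumab. That row was updated in the current amendment and is where Section 12.1.3.1 already points.

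The third change has a downside: it replaces a permanent pembrolizumab stop at first Grade 3 with withholding. If the sponsor intends the stop, it should go into the Table 12.1-2 row instead.

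The cost is one paragraph and one table row (or two rows under that alternative), by amendment or clarification letter, with no added data or patients.
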